10.2 Safety Monitoring Plan

The NHLBI Gene and Cell Therapy Data Safety Monitoring Board provided oversight for the conduct of this trial from July 2013 to September 2016. Safety monitoring oversight was transferred to the UCLA Clinical and Translational Science Institute (CTSI) DSMB in September 2016.

10.2.1 Safety Review Plan by the DSMB / SMC

Reports will be submitted to the DSMB using their established guidelines, which will include latest protocol version, confirmation of RAC, IBC, and IRB approval, enrollment numbers, update of subjects, status of the study, and timelines.

11 STATISTICAL CONSIDERATIONS

11.1 Background

The objectives of the statistical analyses described in this section are to demonstrate the safety and efficacy of the fresh formulation of OTL-101, an autologous, genetically modified CD34+ Hematopoietic Stem Cells (HSC) for the treatment of severe combined immunodeficiency due to

adenosine deaminase deficiency (ADA-SCID). Full details of the planned statistical analyses for this study are found in the statistical analysis plan.

11.2 Design Considerations and Data

This is a subject-level historically controlled, prospective, non-randomized Phase I/II clinical trial to assess the safety and efficacy of autologous transplantation of CD34+ cells originated from the bone marrow of ADA-SCID infants and children following human ADA cDNA transfer by the EFS-ADA lentiviral vector.

Descriptive results will be presented for the study cohort.

Comparisons will be made to three cohorts:

- 1) A historical control group consisting of ADA-SCID HSCT-treated subjects lacking a medically eligible HLA-matched sibling/family donor and treated at GOSH/UCL (UK) or Duke University Children's Hospital, North Carolina Transplant Center (USA) from the year 2000 onward
- 2) A historical control group consisting of ADA-SCID HSCT-treated subjects having a medically eligible HLA-matched sibling/family donor and treated at GOSH/UCL (UK) or Duke University Children's Hospital, North Carolina Transplant Center (USA) from the year 2000 onward
- 3) All HSCT-treated subjects from GOSH/UCL or Duke University Children's Hospital, who were treated with HSCT from the year 2000 onward, with any type of donor

Details on the historical HSCT control groups from GOSH/UCL and Duke University Children's Hospital can be found in [Appendix H](#).

Statistical analyses will be performed, and their outcomes presented, in three stages:

- Interim look – 6 months
 - Descriptive statistics for all available subjects
- Primary analysis - Comparison on primary efficacy endpoints to the HSCT control cohorts—12 month follow-up analysis
 - Descriptive statistics for the complete study cohort, with all patients having reached at least 12 month follow-up
 - Comparison to HSCT control cohorts on safety, primary efficacy endpoints and need of immunoglobulin replacement (IgRT) (main secondary efficacy endpoint).
- End of study analysis:
 - Descriptive statistics for the complete study cohort, with all patients having completed the study (24-month follow-up)
 - Comparison to HSCT control cohorts on safety, primary efficacy endpoints and need of immunoglobulin Replacement (IgRT) (main secondary efficacy endpoint).

In each study stage and for all analyses, all relevant data available will be used.

11.3 Endpoints

Study endpoints are provided in [Section 4.2](#). A brief summary of study endpoints is provided below.

11.3.1 Safety

Safety endpoints in this study are AEs, including SAEs, with intensity/severity graded by Common Terminology Criteria for Adverse Events (CTCAE) criteria, including relation to treatment. Special attention will be paid to the following AE types:

- Clinical toxicities
- Exposure to replication-competent lentivirus (RCL)
- Development of monoclonal expansion or leukoproliferative complications from vector insertional effects.

11.3.2 Primary Efficacy

The primary efficacy endpoints in this trial are OS and EvFS at 12 months.

11.3.3 Secondary Efficacy

The secondary efficacy endpoints in this trial fall under the following outcome categories

- Overall survival and event free survival at 24 months
- Efficacy of gene transfer/engraftment of HSC
- ADA expression, enzyme activity and detoxification
- Effects of ADA reconstitution on immune phenotype and function – note that need of IgRT will be assessed under this category
- Immune reconstitution
- Infection rates

11.4 Sample Size Considerations

Due to the ultra-orphan nature of this indication, the number of subjects for this trial is planned based on practical considerations. Specifically, the number of ADA-SCID children meeting eligibility criteria in the catchment area is expected to be 4-5 per year. Thus, N = 20 subjects is a reasonable enrollment number for a completion of the trial in a reasonable timeframe.

It should be noted that N = 20 will provide precision of 7% for 100% success (survival) at any particular time point and 12% precision if one failure is observed in the 20 subjects. Precision is here defined as the half-width of the two-sided 95% CI using the Exact Binomial computations.

In summary, 20 subjects receiving OTL-101 will participate in this trial.

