Lentiviral vectors have entered the clinic in a trial with HIV-1-infected subjects (performed by investigators from VirXSys Corp. and the University of Pennsylvania) ([Levine, 2006](#)). This study targeted mature T cells collected by apheresis for *ex vivo* transduction with a lentiviral vector encoding antisense RNA to HIV-1 *env* sequences. There was relatively effective gene delivery to the T cells, with ongoing detection of gene-modified T cells for more than one year in two of the subjects. Follow-up over two years did not detect adverse clinical effects.

Lentiviral vectors to transduce CD34+ HSC are only recently entering human clinical trials. One trial to use a lentiviral vector to introduce a shRNA into G-CSF mobilized PBSC to down-regulate the HIV-1 co-receptor CCR5 yielded only very low levels of gene-containing peripheral blood cells ([Zaia, 2009](#)). Importantly, in a recently reported clinical trial of gene therapy for X-linked

adrenoleukodystrophy, the first to use a lentiviral vector to transduce CD34+ PBSC and which used full cytoablative conditioning, 10-20% gene marking was obtained in all blood cell lineages both subjects for at least one year ([Cartier, 2009](#)). One subject in a clinical trial in France using a lentiviral vector carrying a human beta-globin expression cassette attained up to 10% gene marking and clinical improvement to the point of becoming transfusion-independent ([Cavazzana-Calvo, 2010](#)).

As of October 2016, 20 patients have been treated at UCLA with OTL-101, and the trial is closed to enrollment. At last analysis cut-off date (31 March 2016), 18 evaluable patients have 100% overall survival and 100% event-free survival (defined as not returning to ERT or requiring a rescue HSCT). Additionally, 15 evaluable patients (of 18 patients total, including compassionate use patients) have been treated with the related product at Great Ormond Street Hospital (GOSH)/University College London (UCL) with 100% overall survival and 93.3% event free survival. At UCLA all of the patients with sufficient follow-up have also stopped immunoglobulin replacement therapy (IgG RT) and all but one has stopped at GOSH/UCL.

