8.3.1 Primary Efficacy Endpoints

8.3.1.1 Overall Survival at 12 Months

Overall survival will be evaluated using the time in months from transplant to either the subject's death or their last evaluation calculated as:

12*(date of death/last evaluation – date of transplant)/365.25,

or, for HSCT control subjects for whom the dates were not recorded, as:

age in months at death/end of follow-up - age in months at transplant.

The number (%) of subjects who were still alive at 12 months post-transplant will be summarised. For the purpose of this analysis, any subject who withdrew from the study prior to 12 months, who was known to be alive at the last evaluation, will have a status of "unknown". The proportion and exact 95% confidence interval (CI) for survivors at 12 months post-transplant will be calculated for the OTL-101 treated and each of the HSCT control groups along with the difference in proportions (with 95% CI) between the OTL-101 treated and each of the control groups, excluding those with unknown status.

Final Version 4.0 Page 17 of 27

Overall survival in each treatment group will also be presented using a Kaplan-Meier curve for time to death. For the purpose of this analysis, any subject who withdrew from the study prior to 12 months and was known to be alive at the last evaluation will be censored at the date of their last evaluation. If appropriate, the proportion alive at 12 months and the associated 95% confidence interval will be estimated for each treatment group from the Kaplan-Meier curve along with the median survival time (and interquartile range), if they can be estimated from the data.

If there is at least one event in each group, the log-rank test will be used to compare the difference in survival curves between the OTL-101 treated subjects and each of the HSCT control groups.

In addition, a Bayesian analysis will be carried out. The prior distribution for the rate of survivors in each treatment group will be set to Beta(α =1, β =1) (a conservative non-informative prior). The number of survivors in each group (X) will be estimated and the posterior distribution for the rate of survivors in each group will be updated to Beta(α =1 + X, β =1 +N - X), where N is the total number of subjects in the group. Histograms will be presented for the posterior distributions for each treatment group.

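### The 7% precision for 20 of 20 successes in Protocol 11.4 should be 8.4% under the protocol's own definition

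*Protocol*

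**What the plan says.** Protocol 11.4 sets the sample size on feasibility: "the number of subjects for this trial is planned based on practical considerations", with 4 to 5 eligible children expected per year. It then adds two precision figures as a remark. The first is that "N = 20 will provide precision of 7% for 100% success (survival) at any particular time point". The second is "12% precision if one failure is observed in the 20 subjects". One definition covers both: "Precision is here defined as the half-width of the two-sided 95% CI using the Exact Binomial computations". No separate rule is given for the case of no failures.

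The SAP does not repeat these figures. Section 8.3.1.1 plans the matching interval for the primary endpoint: "The proportion and exact 95% confidence interval (CI) for survivors at 12 months post-transplant", leaving out subjects whose status is unknown. Section 8.3.1.2 treats event-free survival in the same way.

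**The concern.** Two figures in one sentence share one definition, so both should come out of the same calculation. One does and the other does not. The one that fails is stated as more precise than the design delivers.

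It is also the figure a reader may well look up. Protocol 2.1.6.2 reports that at the 31 March 2016 cut-off "18 evaluable patients have 100% overall survival and 100% event-free survival". That text gives no follow-up time and covers 18 patients rather than 20, so it does not settle the 12-month result, but it makes a result with no failures plausible. If all 20 subjects succeed and are evaluable, a standard exact 95% interval will be wider than section 11.4 promised.

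**Working it through.** **Inputs.** All come from Protocol 11.4: N = 20; a two-sided 95% exact binomial interval, so 2.5% per tail; precision equal to half the interval's width; stated values of 7% for 20/20 and 12% for 19/20.

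**Step 1: the figure that reproduces (19/20).** The exact (Clopper-Pearson) limits are beta quantiles.

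- Lower limit: 2.5% quantile of Beta(19, 2) = 0.7513.
- Upper limit: 97.5% quantile of Beta(20, 1) = 0.975^(1/20) = 0.9987.
- Half-width: (0.9987 − 0.7513)/2 = 0.1237, or 12.4%.

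This agrees with the stated 12%, so the definition is being read as it was applied there. As a check, the binomial tail probability at each limit is 0.025.

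**Step 2: the figure that does not (20/20).** When every subject succeeds, the upper limit is 1 and the lower limit L solves L^20 = 0.025.

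- L = 0.025^(1/20) = 0.8316.
- Half-width: (1 − 0.8316)/2 = 0.0842, or 8.4%.

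This rounds to 8%, so rounding does not explain 7%. The excess over the stated value is 8.42 − 7 = 1.42 percentage points. In terms of the lower limit, a half-width of 7% below an upper limit of 100% implies 100 − 2 × 7 = 86%, against 83.2%.

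**Step 3: could another method give both figures?** Half-widths at nominal 95% unless noted:

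| Method | 20/20 | 19/20 |
|---|---|---|
| Stated in Protocol 11.4 | 7% | 12% |
| Exact, two-sided 95% | 8.4% | 12.4% |
| Exact, two-sided 90% | 7.0% | 10.7% |
| Mid-p | 7.0% | 11.0% |
| Wilson | 8.1% | 11.4% |
| Uniform-prior Bayes | 8.0% | 11.3% |
| Sterne | 8.3% | 12.1% |
| Jeffreys | 5.8% | 10.3% |
| Agresti-Coull | 11.1% | 13.2% |
| Wald | 0% | 9.6% |

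None of these, applied to both cases, gives 7% and 12% together. The 7% equals the result with 5% in the lower tail: 0.05^(1/20) = 0.8609 and (1 − 0.8609)/2 = 0.0696. With 5% in each tail, the second figure would be 10.7%, which rounds to 11% and not 12%.

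**Step 4: what would give 7% under the stated definition?** With no failures, N = 24 gives a half-width of 7.1% and N = 25 gives 6.9%. N = 20 does not reach it.

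**The case against.** The best defence is a boundary convention. At 20/20 the upper limit is fixed at 100%, so the interval can miss on one side only. Some analysts then put the whole 5% in the lower tail, which gives 86.1% and a half-width of 6.96%. At 19/20 both tails are open, and 2.5% in each gives 12.4%. On that reading both stated figures hold at 95% confidence. This is a plausible account of how the 7% arose, and the convention itself can be defended. It does not rescue the sentence as written, because the definition says two-sided for both figures and mentions no exception. The documents do not say how the 7% was obtained.

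Two further points stand. First, the practical weight is very small. Protocol 2.1.6.2 says that 20 patients have been treated and enrolment is closed, so the figure can no longer influence the design. Second, the mismatch with the eventual report is conditional. The SAP names neither the exact method nor a boundary rule, and its exclusion of unknown status could bring the denominator below 20.

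**Conclusion.** The 7% is wrong under the definition that the protocol attaches to it. The correct half-width for 20/20 is 8.4%, about 1.4 percentage points larger, and the exact interval is 83.2% to 100%. The 12% for one failure stands.

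This rests on reading the exact binomial interval as the standard equal-tailed one, which is the reading that reproduces the 12%. The severity is minor. The sample size does not derive from the figure. No test, stopping rule or margin uses it, including the 10% margin in the SAP's Bayesian comparison. The SAP intervals will be computed from the observed data.

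**What to change.** Restate the precision sentence in Protocol 11.4 along these lines: with 20 subjects, the exact two-sided 95% confidence interval is 83.2% to 100% (half-width 8.4%) if all succeed, and 75.1% to 99.9% (half-width 12.4%) if one fails. Giving the limits as well as the half-widths lets any reader check them.

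If a one-sided 95% limit was intended when no failure occurs, the alternative is to say so in 11.4 and to state the same rule in SAP 8.3.1.1. Correcting the figure is simpler, since it keeps the existing definition and adds no convention.

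The cost is one sentence and a slightly less favourable number. The sample size, analyses and conduct of the trial are unchanged.

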11.5 Analysis Sets

11.5.1 Safety Analysis Set

The safety analysis set will consist of all patients treated with OTL-101 at UCLA/NIH (current study cohort) and the complete HSCT historical control cohort, consisting of ADA-SCID subjects with any type of donor treated with HSCT at either GOSH/UCL (UK) or Duke University Children's Hospital (USA) from the year 2000 onward.

11.5.2 Full Analysis Set

The full analysis set will consist of all patients treated with OTL-101 at UCLA/NIH (current study cohort).

The primary analysis set for efficacy from the HSCT historical control cohort will consist of ADA-SCID patients without a medically eligible HLA-matched sibling/family donor and treated with HSCT at either GOSH/UCL or Duke University Children's Hospital from the year 2000 onwards.

Additional efficacy comparisons will be made with:

- ADA-SCID patients with matched related donors treated with HSCT at either GOSH/UCL or Duke University Children's Hospital from the year 2000 onwards;
- the complete HSCT historical control cohort consisting of ADA-SCID patients with any type of donor treated with HSCT at either GOSH/UCL or Duke University Children's Hospital from the year 2000 onwards.

Note however that for the analysis of primary efficacy, full EFS data for HSCT subjects might only be available for the 12-month (primary) and 24-month (end of study) analyses.

11.6 Statistical Methods

11.6.1 Overview

As noted in [Section 11.2](#), the statistical analysis of this data will be done in three stages, which are presented below in [Sections 11.6.2](#), [11.6.3](#) and [11.6.4](#). Since all analyses repeat themselves in the different stages, each will be described in detail the first time it appears, which will be referred to in subsequent sections where it is repeated.

The data will be summarized in tables displaying the mean, standard deviation, median, minimum, maximum and number of subjects per group for continuous data (e.g. age, weight) or in tables displaying count and percentage for categorical data (e.g. gender, previous treatment). Data will be presented by visit, if applicable. Data listing by subject will be provided and, where applicable, presented graphically.

Statistical analyses will be performed and data appendices created with SAS® V9.4 or higher.

11.6.2 Interim Look

The interim look will include subjects from UCLA OTL-101 (all subjects followed for at least 6 months) and aggregate data from HSCT treated subjects treated at GOSH (N ~ 25). The following sections describe analyses for both groups, although EvFS and most secondary endpoints may not be available for the HSCT historical controls at this stage of the analysis.

11.6.2.1 Subject Disposition

Subject disposition will be done on the safety analysis set, with disposition provided by UCLA, and all HSCT subject groups. Subject disposition will be tabulated; the number of enrolled, exposed, prematurely terminated, ongoing and completed subjects will be summarized. A list of dropouts will be prepared including treatment received, reason for discontinuation, and time of discontinuation.

11.6.2.2 Baseline Characteristics

Baseline characteristics will be done on the safety analysis set, with characteristics presented by UCLA, and all HSCT subject cohorts. The following information collected at baseline will be presented:

- Demographics (Age, Gender, etc.)
- Method of diagnosis
- Whether received previous HSCT including: date, transplant cells, donor type and outcome
- Whether received previously PEG-ADA. If yes, for how long
- Whether received previously or is receiving currently immunoglobulin replacement therapy
- Listing of relevant medical history, including infections

11.6.2.3 Safety Analyses

Safety will be analyzed descriptively by arm over time for the safety population. Coding will be done using current MedDRA version or higher. AEs, including SAE's will be presented by:

- System organ class and preferred term

Where appropriate, shift tables will be presented for laboratory parameters, vital signs and physical examination.

11.6.2.4 Efficacy Analyses

11.6.2.4.1 Primary Efficacy Analyses

The primary efficacy endpoints, overall survival (OS) and event free survival (EvFS), will be analyzed descriptively, including frequencies for each type of event for EvFS. Additionally, the following analyses will be done to present and compare the treatment arms, OTL-101 subject and HSCT historical control groups, so as to provide as complete a picture as possible of efficacy given the small sample size:

1. OS and EvFS will be described using Kaplan-Meier curves for time to death/event by treatment arm, and a comparison between arms made using the log-rank test.

- OS and EvFS rates at 12 months (for those subjects who have reached the 12-month time point) will be described by arm and the difference between arms presented along with associated exact binomial CIs.

11.6.2.4.2 Secondary Efficacy Analyses

Main Secondary Endpoint

- Overall survival and event free survival at 24 months
- Use of immunoglobulin replacement therapy.

Additional Secondary Endpoints

The following will be presented for the infection endpoint:

- Frequency table for number and percent of patients who experienced 0, 1, 2, or at least 3 infections,
- Rate of infection will be calculated on the basis of person-years.

11.6.3 Primary Analysis

The primary analysis will include data from the current study where all subjects have reached the 12-month time point, HSCT historical controls (with or without HLA-matched related sibling donor, evaluated separately and together).

The following analyses will be repeated, as described in preceding sections:

- Subject disposition ([Section 11.6.2.1](#))
- Baseline characteristics ([Section 11.6.2.2](#))
- Safety ([Section 11.6.2.3](#))
- Efficacy ([Section 11.6.2.4](#))

11.6.4 End of study Analysis

The end of study analysis will repeat the analyses for the preceding section ([Section 11.6.3](#)) for the study cohort in which all subjects are expected to have completed 24 month follow-up.

11.7 Safety Review

11.7.1 Stopping Rules for the Protocol

If any of the following five instances occur, the protocol will be stopped, pending investigation of the cause. Findings will be discussed with the FDA, IRB and DSMB before enrolling the next patient. Study endpoints of subjects already enrolled will continue to be obtained.

1. If there is one death, or four grade 4 toxicities, not Busulfan-related (transient leukopenia, anemia, thrombocytopenia resolving within 42 days of transplant, which are anticipated and will be reported, will not be considered stopping criteria). Additionally, neutropenia (a

documented disorder of ADA-deficiency) occurring at any time, will be graded for severity but will not count towards the stopping rule.

2. If two subjects have prolonged pancytopenia, defined as at least any two of the following (ANC < 200mm³, and/or platelets < 20,000mm³ without transfusions, and/or Hb < 8.0 g/dL without transfusions) on three independent and consecutive determinations over at least ten days beyond day +42 after CD34+ cell infusion.
3. If 0 of 3 successive patients show evidence of engraftment of transduced cells by six months of follow-up (all peripheral blood samples negative by PCR for vector sequences or by ADA enzyme assay).
4. If RCL is detected, and confirmed, in one subject.
5. If a subject in this study develops hematological proliferative, monoclonal expansion or malignant disease (excluding DFSP), active enrollment of further subjects will be placed on hold. A thorough investigation of the cause of the proliferation, expansion or malignancy, including proviral integration analyses, will be done.

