nutritional support), consequences of toxicity to Busulfan, engraftment of transduced cells and immune reconstitution. Alternatively, for out of town subjects who are clinically stable, post-transplant care may be transferred to the home physician provided they have agreed to assume the post-transplant monitoring. The monitoring can take place as an in-patient or as an outpatient. In this case, the subject will stay a minimum of 3 days after infusion of the cells at the treatment facility (UCLA or NIH) prior to being transferred. This planned discharge and subsequent re-admission to a second facility would not constitute an adverse event.

PEG-ADA will be stopped on day +30 post-cell product infusion if the patient received busulfan and the final cell product and does not have active infections or other major medical problems.

For subjects who have slow recovery of counts after transplant (beyond Day +30), CBC/Diff will be performed at least once every 7-10 days, until ANC is >500 cells/mm³. If after day +42 the criteria for non-engraftment are met (persistent ANC $< 200/\mu\text{l}$ or platelets $< 20,000/\mu\text{l}$) after cell infusion on three independent and consecutive determinations over at least ten days, the back-up cells will be given. If hematologic reconstitution does not occur by Day +90 from the initial infusion of the cell product, prolonged unresponsive pancytopenia will exist.

Infection prophylaxis: The subjects will be maintained on prophylactic antibiotics and intravenous gamma-globulin replacement and will be closely monitored as an outpatient. They will be readmitted to a hospital when deemed clinically necessary. These reasons include, but are not limited to: fever and neutropenia, bacteremia, possible central venous access device infection, or other infections that require initial parenteral antibiotics, organ failure, extreme adverse social situations, and/or bleeding.

Prophylactic antibiotics will be used to provide coverage for *Pneumocystis jirovecii* pneumonia and mucosal yeast:

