9.9 Halting Rules for the Protocol

If any one of the following five instances occurs, new enrollment to the protocol or treatment of subjects will be halted, pending investigation of the cause. Findings will be discussed with the FDA, IRB and DSMB and each must agree to conditions by which the study can be resumed before enrolling the next patient. Evaluations of study endpoints of subjects already enrolled and who received the final cell product will continue to be performed.

1. If there is one death or four grade 4 toxicities (except grade IV busulfan-related hematologic serious adverse events {transient leukopenia, anemia, thrombocytopenia resolving within 42 days of transplant} which are anticipated and will be reported, but will not be considered stopping

criteria). Additionally, neutropenia (a documented disorder of ADA-deficiency) occurring at any time, will be graded for severity but will not count towards the stopping rule.

2. If two subjects have prolonged unresponsive pancytopenia. This is defined as initial failure at hematologic reconstitution which does not improve following administration of the back-up marrow. Failure of hematologic reconstitution is defined as at least any two of the following being: ANC $<200/\text{mm}^3$, and/or platelets $< 20,000/\text{mm}^3$ without transfusions, and/or Hb $< 8.0 \text{ gm/dl}$ without transfusions) on three independent and consecutive determinations over at least ten days beyond day +42 from initial infusion of the cell product. If these conditions are reached, the back-up marrow will be infused IV. If failure of hematologic reconstitution persist after the back-up marrow has been given through day +90 from the initial infusion of the cell product, prolonged unresponsive pancytopenia will exist.

3. If 0 of 3 successive patients show evidence of engraftment of transduced cells by six months of follow-up (all peripheral blood samples negative by ddPCR/qPCR for vector sequences ($<1/10,000$) or by ADA enzyme assay).

4. If RCL is detected, and confirmed in one subject.

5. If a subject in this study develops hematological proliferative, monoclonal expansion or malignant disease (excluding DFSP). A thorough investigation of the cause of the proliferation, expansion or malignancy, including proviral integration analysis, will be done.

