14.5 Timing/Reports

Data and reports are reviewed at least every 1-3 weeks at meetings with trial personnel at the coordinating site. Joint teleconferences between UCLA and the NIH will be held once every 1 or 2 months (as schedules allow). Data from CRFs are compiled quarterly for analysis by the

Biostatistics group, and these analyses are reviewed by the Sponsor and trial biostatistician quarterly to monitor for stopping rule criteria.

Routine reports to regulatory agencies are periodic: biannually to the DSMB (based on their schedule) and yearly to the IRB, FDA, OBA RAC and DAIT, NIAID. Final study reports will be generated at the completion of the study. No data is masked and data is coded only for the purposes of presenting the study to the public. A master list, which is only accessible to study personnel, will be kept to match the individuals to their coded PIN.

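### The protocol states its halting rules twice, and two subjects who recover after back-up marrow meet the pancytopenia rule in Section 11.7.1 but not the one in Section 9.9

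*Protocol*

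**What the plan says.** Protocol Sections 9.9 (Halting Rules for the Protocol) and 11.7.1 (Stopping Rules for the Protocol) each set out five trial-level rules. Both are current text. The SAP as supplied has no section on halting rules.

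**Pancytopenia (item 2).** Section 11.7.1: "If two subjects have prolonged pancytopenia, defined as at least any two of the following", followed by ANC, platelet and Hb limits, three determinations, a span of at least ten days, and day +42. The definition ends there. Section 9.9 uses the same limits and the same two-of-three criterion, but its halting event is "initial failure at hematologic reconstitution which does not improve following administration of the back-up marrow", and the failure must persist through day +90.

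**Grade 4 toxicity (item 1).** Section 9.9 counts four grade 4 toxicities "except grade IV busulfan-related hematologic serious adverse events". Section 11.7.1 counts "four grade 4 toxicities, not Busulfan-related", then lists transient cytopenias in a parenthesis.

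**Resumption.** Section 9.9 makes resumption depend on the agreement of FDA, IRB and DSMB, each of them. Section 11.7.1 asks only that findings be discussed with them.

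**Back-up cells.** Section 7.4 gives back-up if after day +42 "the criteria for non-engraftment are met", meaning persistently low ANC or platelets. Section 6.1 D and Appendix B (C2) also use ANC or platelets. Section 9.9 gives back-up when its two-of-three condition is reached.

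**Monitoring.** Under Section 14.5 the compiled data are "reviewed by the Sponsor and trial biostatistician quarterly to monitor for stopping rule criteria". It does not say which list is meant.

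**The concern.** A halting rule should give one answer for one set of data. Here the pancytopenia rule has two complete definitions in the same protocol, and the added condition in 9.9 (no response to back-up) decides the answer in just the case where back-up works.

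Safety is a primary objective, and the final report will probably say whether any halting rule was met. With two definitions that sentence has no fixed meaning: one reader could apply 11.7.1 and another 9.9 to the same counts and disagree, each with the protocol in hand.

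**Working it through.** The documents give no halting probability or other operating characteristic for these rules, so there is no stated figure to reproduce. The check is a comparison of texts, a listing of possible subject states, and an illustration on assumed rates.

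**1. Side by side**

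| Element | Section 9.9 | Section 11.7.1 |
|---|---|---|
| Subjects needed for pancytopenia | 2 | 2 |
| Counts | any two of ANC, platelets, Hb | the same |
| Confirmation | three determinations, at least ten days, beyond day +42 | the same |
| Response to back-up | must fail to improve | not mentioned |
| End point in time | persists through day +90 | none |
| Grade 4 exemption | busulfan-related, hematologic | busulfan-related, with cytopenias in parenthesis |
| Death trigger, count of four, 42-day limit, neutropenia exclusion | present | the same |
| Before resuming | each body must agree | discussion |

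**2. Subject states.** Let ANC, platelets and Hb each be below the limit or not after day +42, and let the subject recover after back-up by day +90 or not: 2 × 2 × 2 × 2 = 16 states.

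- At least two of three low: 3 + 1 = 4 patterns, × 2 for recovery = 8 states. All 8 count under 11.7.1.
- Only the 4 without recovery count under 9.9.
- So 8 − 4 = 4 of 16 states count under 11.7.1 alone, and none counts under 9.9 alone. Two subjects in any of those 4 states stop the protocol under one section and not the other.

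**3. Timing.** Section 11.7.1 needs at least ten days beyond day +42, so its earliest decision is about 42 + 10 = day +52. Section 9.9 cannot be decided before day +90. The gap is 90 − 52 = 38 days.

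**4. Back-up trigger.** Any two of three lineages must include ANC or platelets, so every subject who meets the 9.9 condition also meets the one in 7.4. ANC alone or platelets alone (2 patterns × 2 = 4 states) calls for back-up under 7.4 and does not reach the 9.9 condition. Section 9.9 does not say that back-up is withheld from such a subject. In 2 of those 4 states (no recovery by day +90), 7.4 can attach the label *prolonged unresponsive pancytopenia*, which is the name of the 9.9 halting event, although the two-of-three definition is not met.

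**5. Illustration on assumed rates.** Let p be the chance that a subject meets the counts after day +42 and r the chance of recovery after back-up. Neither is in the documents. With 20 independent subjects, P(at least 2) = 1 − (1 − q)^20 − 20q(1 − q)^19, where q = p under 11.7.1 and q = p(1 − r) under 9.9. For p = 0.05, 11.7.1 gives 1 − 0.3585 − 0.3774 = 0.264. With r = 0.5, q = 0.025 and 9.9 gives 1 − 0.6027 − 0.3091 = 0.088.

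| Assumed p | 11.7.1 | 9.9, r = 0.5 | 9.9, r = 0.8 |
|---|---|---|---|
| 5% | 0.264 | 0.088 | 0.017 |
| 10% | 0.608 | 0.264 | 0.060 |
| 20% | 0.931 | 0.608 | 0.190 |

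If nobody recovers (r = 0) the two rules agree. The table shows only that the added condition is not a technicality; it says nothing about what happened in this trial.

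**The case against.** The best defence is that 9.9 is the operative rule and 11.7.1 a shortened restatement. The text does not say so. Section 11.3 openly calls its endpoint list a summary and points to Section 4.2, whereas 11.7.1 has no such pointer and gives a complete definition of its own. The pancytopenia conflict stands.

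Other objections succeed, and they limit the point:

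- **Grade 4.** A reader might infer a flat contradiction. The parenthesis in 11.7.1 can fairly be read as defining the exemption, and then the two versions nearly agree. The change log for version 8 records one change to this rule, with the hematologic wording, on pages that appear to cover both sections, which suggests one intended rule. What remains is loose wording. Read literally, a grade 4 liver enzyme elevation from busulfan (an anticipated effect under Section 9.5.2.4) counts under 9.9 and not under 11.7.1.
- **Back-up.** A reader might infer that the sections give opposite instructions. They do not: the 9.9 condition is sufficient for back-up and is contained in the ANC-or-platelets trigger. It matters only because 9.9 builds response to back-up into its halting event and 7.4 shares the label.
- **A single event.** A reader might infer that one subject's event both halts and does not halt the trial. Both versions need two subjects, so the conflict arises with the second.
- **48 days.** Subtracting day +42 from day +90 overlooks the ten-day span in 11.7.1.
- **Misreporting.** A reader might infer that the DSMB was misinformed or a rule breached. Nothing in the documents shows either. Grade 3 and 4 events go to the sponsor within 48 hours whatever their relation to treatment (Section 9.5.1), and all SAEs go to the DSMB regardless of causality (Section 9.5.2.3).
- **Practical effect.** Both rules act on enrolment or treatment, and follow-up continues under both. Section 2.1.6.2 says that 20 had been treated and enrolment was closed as of October 2016, so all had passed day +90 well before version 12 of March 2018. No future accrual depends on this.

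**Conclusion.** The pancytopenia halting rule is contradictory as written. It separates 4 of 16 subject states, always in the direction that 11.7.1 counts a subject and 9.9 does not, and the earliest decisions lie about 38 days apart. The response condition, rather than the day count, is the substantive difference.

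The grade 4 wording and the resumption condition are lesser differences. On the literal reading of grade 4, 9.9 is the wider rule, so neither section is stricter throughout and choosing the stricter section does not settle matters.

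The conclusion rests on the current text alone; the assumed rates carry no weight in it. Whether any of the 20 subjects met either version cannot be told from the documents. With enrolment closed, the consequence is confined to the safety monitoring record and to how the report states whether a halting rule was met.

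**What to change.** 1. Reconcile Sections 9.9 and 11.7.1 into one statement of the halting rules and have the other section refer to it. This covers the pancytopenia definition, the scope of the grade 4 exemption and the condition for resuming. Which clinical threshold is right is for the sponsor, investigators and DSMB; this review does not choose.
2. In the same edit, align the wording of the back-up trigger in Sections 6.1 D, 7.4 and 9.9 and Appendix B, and make the day +90 label in 7.4 agree with the definition of the halting event.
3. State in Section 14.5, or in a note to file, which version governed the quarterly monitoring.
4. Check the 20 treated subjects once against each written version and report the result for both, so that any statement on halting rules can be read only one way.

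The cost is a text amendment and a single review of data already held: Appendix B schedules blood counts at least every 7 to 10 days for subjects slow to recover beyond day +30, until ANC exceeds 500. No new data collection and no change to the efficacy analysis are needed.
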